6 STUDY PERIODS, TREATMENT REGIMENS AND POPULATIONS FOR ANALYSES

6.1 Study Periods

Study CV181-369 consists of 4 study periods:

- 1) **Screening period (Period A).** This period starts with enrollment (i.e., signature of the protocol-specific informed consent form constitutes the first procedure of the Screening period) and ends on the start of lead-in period. Subjects should be on a stable dose of metformin 1500 mg/day for at least 8 weeks prior to screening visit with or without a stable dose of a SU of at least 50% the maximal dose per local label.
- 2) **Lead-in period (Period B).** During this period, subjects will continue their diabetes management with stable dose of metformin 1500 mg/day with or without a stable dose of SU, diet and exercise. No placebo or study medication will be provided during the lead-in period.
- 3) **24-week short-term open-label treatment period (Period C).** On the Day 1 visit, subjects who meet all the protocol-specific enrollment and randomization criteria will be randomized.
- 4) **28-week long-term open-label treatment period (Period D).** After completing the short-term period, subjects will enter the 28-week open-label long-term treatment period. The start date of long-term treatment period is defined as the end date of short-term treatment period. This is the date when the subject entered the long-term treatment period and was dispensed long-term study medication.

Follow-up non-treatment phase (Period X). Subjects who discontinue study treatment early will follow the same visit schedule as subjects who remain on treatment.

6.2 Treatment Regimens

On the Day 1 visit, subjects who meet all protocol enrollment and randomization criteria will be randomized into one of the two open-label treatment arms, in a 1:1 ratio:

- Saxagliptin 5 mg QD and Dapagliflozin 10 mg QD
- Titrated insulin glargine

Randomization will be stratified by current use of background medication (metformin alone vs. metformin plus SU) at baseline to ensure equal representation across all treatment groups and also within the sub-study. Subjects will continue to receive their stable dose of metformin with or without SU throughout the study. The “as randomized” treatment group is defined as the treatment group to which a subject was randomized at the start of the open-label treatment period (even if the treatment they received was different). The primary efficacy analyses will be performed using the Randomized Subjects Data Set.

The “as treated” treatment group is the same as the “as randomized” treatment group, except in cases where information was available which indicated that a subject received a different treatment for the

entire course of their participation in the study (or period). In this case, the “as treated” treatment group is set to the treatment the subject actually received. In case a subject never received the treatment as assigned by randomization, then the “as treated” treatment group is the first treatment received.

6.3 Populations for Analyses

6.3.1 *Enrolled Subjects Data Set*

This consists of all subjects who signed informed consent.

6.3.2 *Lead-in Subjects Data Set*

The lead-in subject data set includes data collected from all subjects who have at least one vital sign measurement during Lead-in Period.

6.3.3 *Randomized Subjects Data Set*

The randomized subject data set will consist of all randomized subjects who receive at least one dose of study medication. Whenever using the randomized subject data set, subjects will be presented in the treatment group to which they were randomized at the start of the Short-term treatment Period (even if the treatment they received was different). This is also known as the Intent-to-Treat (ITT) population. This will be the primary efficacy data set.

6.3.4 *Full Analysis Set*

The full analysis set (FAS) is defined as all randomized subjects who take at least one dose of the study medication and have a baseline value for HbA1c. Analysis of the FAS will be based on the randomized treatment.

6.3.5 *Evaluable Subjects Data Set*

The Evaluable Subjects Data Set will be a subset of the Randomized Subjects, with all data points collected after a relevant protocol deviation excluded from the data set. Relevant protocol deviations are defined as deviations that could potentially affect the interpretability of the study results. This is also known as the Per-protocol population. All decisions to exclude patients and/or data from the Randomized Subjects Data Set will be made prior to un-blinding the study and agreed by the study team.

6.3.6 *Treated Subjects Data Set*

The Treated Subjects Data Set for ST and ST+LT will consist of all subjects who receive at least one dose of study medication during the short-term treatment period. This will be the primary safety data set. Data in this data set will be analyzed based on randomized treatment, except in cases where a subject received a different treatment for the entire course of his/her participation in the treatment period. In this case, safety data for such a subject will be analyzed based on the first treatment the subject actually received.

6.3.7 *Short-term Completers Data Set*

The short-term Completers Data Set will consist of all subjects in the Randomized Subjects Data Set who were not rescued, and completed ST treatment and entered the LT treatment period. It is a subset of the Randomized Subjects Data Set.

Whenever using the Short-term Completers Data Set, subjects will be presented in the treatment group to which they were randomized at the start of the ST treatment period (even if the treatment they received in the ST or LT was different).

7 STATISTICAL ANALYSES

7.1 General Methods

7.1.1 Definitions

7.1.1.1 Baseline Value

Unless otherwise stated, for each subject, baseline value of a parameter (e.g., efficacy laboratory parameter, safety laboratory test, ECG or physical measurement endpoint) is defined as the last assessment on or prior to the date of the first dose of the study medication.

7.1.1.2 Change and Percent Change from Baseline

Change from baseline to any Week t in short-term treatment period or ST +LT is defined as follows:

$$C_{\text{Week } t} = M_{\text{Week } t} - M_{\text{baseline}},$$

where:

- $C_{\text{Week } t}$ is the change from baseline at Week t ,
- $M_{\text{Week } t}$ is the measurement at Week t ,
- M_{baseline} is the measurement at baseline.

Percent change from baseline to any Week t in short-term treatment period is defined as follows:

$$P_{\text{Week } t} = 100 \times (M_{\text{Week } t} - M_{\text{baseline}}) / M_{\text{baseline}}.$$

Where $P_{\text{Week } t}$ is the percent change from baseline at Week t , and $M_{\text{Week } t}$ and M_{baseline} are defined as above.

The “Week t ” to which a measurement belongs is determined using the conventions described in Section 8.2 and Section 8.4.

7.1.1.3 Handling of Missing Data

The main analysis for change from baseline specified for primary and secondary endpoints in following sections will use the repeated measures model. For subjects who started rescue medication, measurements taken prior to the date of the first dose of rescue medication will be used. This model assumes that the time course of the endpoint values for subjects who discontinue treatment or are rescued at a specified time point is consistent with the time course for subjects who are ongoing at that time point.

While utilizing models such as ANOVA, for example, in analysis of change (or percent change) from baseline as well as glycemic response endpoint at Week 24 LOCF, the measurement assigned as the Week 24 measurement will be used. If no Week 4 measurement is available (subject has

discontinued before Week 24, or measurement not taken at Week 24, though subject was not discontinued), then the last available earlier post- baseline measurement will be used (LOCF). For subjects who started rescue medication prior to Week 24, their last post-baseline measurement taken prior to the date of the first dose of rescue medication will be used.

Section 8 provides additional information regarding handling of missing or partial dates, inclusion of values, windowing, and values obtained post treatment.

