7.1.8 Proportion of Subjects Achieving Pre-defined Characteristic

Unless otherwise specified, the proportion of subjects *with a pre-defined characteristic* at Week *t* will be analyzed using logistic regression with adjustment for baseline HbA1c value and/or the stratification factor. Subjects in the randomized treatment group who do not demonstrate achieving therapeutic glyceemic response at a specified timepoint or are rescued will count as treatment failures from that timepoint. When proportion of responders (e.g., meeting HbA1c criteria; composite endpoints) is needed, the estimates, confidence intervals, and tests will be obtained using this methodology with adjustment for baseline variable (e.g., adjustment for baseline HbA1c) and stratification factor. For each treatment group, the probability of response is first modeled using a logistic regression model with baseline (e.g., baseline HbA1c) and stratification factor as the covariates. Treatment group estimates of response rate are then obtained by integrating each group's modeled probability of response over the observed distribution of baseline covariate (combined across groups). For analysis of proportion of subjects achieving therapeutic glyceemic response (HbA1c < 7%), the difference in response rate between the saxa-dapa arm and the insulin arm will be displayed along with standard error and 95% confidence intervals using the methodology of Zhang, Tsiatis and Davidian and Tsiatis, Davidian, Zhang and Lu. Non-Inferiority will be demonstrated if the upper bound of the 95% confidence interval is less than 10%.

When there are less than 5 responders in any treatment group, the unadjusted (and difference in) proportions, exact 95% confidence interval, and p-values from the Fisher's exact test (when applicable) will be provided.

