7.5.2 Primary Efficacy Analysis

The primary endpoint is the change in HbA1 from baseline at Week 24 visit. The primary endpoint will be tested for non-inferiority for saxagliptin plus dapagliflozin versus insulin at the $\alpha = 0.025$ level (one sided). The primary analysis of the change in HbA1c from baseline at Week 24 visit will be based on a longitudinal repeated measures analysis using 'direct likelihood'. The model will use subjects in the primary efficacy data set (i.e., randomized subjects data set) who have a baseline assessment and at least one post-baseline open-label

treatment period assessment. The SAS procedure PROC MIXED will be used. The preferred model will include the fixed categorical effects of treatment, week, randomization stratification factor (background medication of metformin alone vs. metformin + SU) and treatment-by-week interaction as well as the continuous fixed covariates of baseline measurement and baseline measurement-by-week interaction (see Model 7.1.2.1 in Section 7.1.2). An unstructured matrix for the within-subject error variance-covariance will be used. The denominator degrees of freedom will be calculated according to the Kenward-Roger method. A number of back-up models are defined in the Core statistical analysis plan (Section 7.1.2) in case of non-convergence of the preferred model or other issues. Data collected outside the analysis window (defined in Section 8 of this SAP) after subjects discontinued study medication will also be excluded from the primary analysis. Point estimates and 95% confidence intervals for the mean change within each treatment group as well as the difference in mean change between the saxagliptin plus dapagliflozin versus insulin will be calculated. If the upper limit of the 95% confidence interval of the difference is $< 0.3\%$, then saxagliptin plus dapagliflozin as add-on therapy to metformin with or without SU will be considered non-inferior to insulin as add-on therapy to metformin with or without SU.

Sensitivity Analyses

The following sensitivity analyses will be carried out for the primary end point:

- Primary analysis will be repeated using Evaluable Subjects data set.
- Primary analysis will be repeated using all available values regardless of rescue or treatment discontinuation
- An ANCOVA analysis using values prior to rescue or treatment discontinuation (LOCF will be used if the week 24 value is not available)

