7.5.3 Handling of missing efficacy data

Missing data in this study may result from patients discontinuing from the study prematurely or missing intermediate visits or selected assessments while remaining on study. Every reasonable effort will be made to obtain the protocol-required data for all study assessments that are scheduled for all patients who have been enrolled. For efficacy analyses, missing observations will not be imputed, except those inherited from the mixed model repeated measures (MMRM) which assumes that data are missing at random (MAR).

MAR refers to missingness that is independent of missing responses, conditionally on observed responses and covariates. As the imputation strategy should always consider the dropout patterns and the time-course of the efficacy measurements by treatment, the pre- and post-withdrawal values will be assessed to understand the impact of dropouts on the efficacy results.

The primary efficacy endpoint of HbA1c data will be visually examined to explore the missingness patterns by (1) plotting each individual patient's HbA1c change trajectory in completers, side-by-side with those from the early study drug withdrawal, and by (2) plotting the early study drug withdrawal's last HbA1c change data, overlaid with the box plot by visit from completer population. Two additional methods of sensitivity analyses will be performed to compare the results from an MAR-based analysis versus an MNAR-based analysis under several MNAR scenarios. The first method is the return-to-baseline using Multiple Imputation in which patients with missing data known or believed to have discontinued protocol therapy were assumed to have a washout ("return to baseline") of any potential treatment effect. More specifically for each imputation of the multiple imputation, for those subject with missing Week 24 measurements for HbA1c. The second method is the Tipping Point Analysis, which assumes that patients from the experimental treatment arm who discontinue treatment or initiate a rescue therapy would have values worse by some amount "delta" compared to efficacy values of similar patients who continue with study treatment and do not require rescue. The detailed analysis plan and implementation of these methods are described in section 7.5.3.1, and 7.5.3.2.

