7.5.5.2 Glycemic Rescue or Discontinuation from Study treatment due to Lack of Efficacy

The proportion of subjects requiring treatment intensification (glycemic rescue or discontinue study treatment for lack of efficacy) up to Week 24 / 52 will be assessed by summarizing the difference in the percentages between treatment groups and by a time-to-event analysis using the Kaplan-Meier methodology.

Time to treatment intensification will be analyzed using a Cox proportional hazards model. Estimates of hazard ratio and 95% confidence intervals will be provided. Kaplan-Meier plots^{□1} of time to intensification at Weeks 24 and 52 will be calculated and plotted by treatment group. Unless otherwise specified, the plot will be presented only when there are at least 10 events in one treatment group. Additionally, a table will accompany the plot and will display the Kaplan-Meier estimates of the cumulative proportion (with 95% CI calculated based on Greenwood's method^{□2} when applicable) of subjects with event at specific time points by treatment group. If the estimated lower bound of 95% CI is below 0 or the estimated upper bound of 95% CI is over 1, then it will be restricted to 0 or 1 respectively. For the analysis during 24 / 52 weeks, all subjects will be censored at Week 24 / 52 visit (end of ST treatment/end of LT treatment) if treatment intensification has not occurred by then. Subjects rescued at Week 24 / 52 will be counted as having an event for the analysis.

Composite response endpoints (glycemic control without hypoglycemia), will be analyzed using logistic regression with adjustment for baseline HbA1c value and/or the stratification factor. None of the exploratory endpoints will be statistically tested

In addition, an analysis of the proportion of subjects not rescued and achieving glycemic response (defined as HbA1c < 7%) in subjects from the Short-term Completers Data Set at time points during the LT period will be performed using the same methodology described above (with adjustment for end of ST HbA1c measurement). Subjects discontinued or missed measurements (regardless of the type of missing) at the specific time point will be considered as not achieving glycemic response.

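### Week 24 HbA1c < 7.0% endpoints (ranked secondaries 3 and 5): the SAP carries unreconciled scoring text for rescued subjects and no clear rule for unrescued subjects without a Week 24 value

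*SAP*

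**What the plan says.** Two ranked secondary endpoints depend on HbA1c < 7.0% at Week 24. The third, response without hypoglycemia, is tested for superiority. The fifth, response alone, is tested for non-inferiority with a 10-point margin. Under section 7.5.1 a failed test stops the sequence, so the third endpoint gates the fourth and fifth.

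Four places in the SAP bear on how a subject is scored:

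- **7.1.1.3.** The paragraph covers models "such as ANOVA, for example, in analysis of change (or percent change) from baseline as well as glycemic response endpoint at Week 24 LOCF". It carries the last earlier post-baseline value forward when the Week 24 value is missing. The trigger reads "If no Week 4 measurement is available", but its own bracket refers to Week 24. For subjects rescued before Week 24, "their last post-baseline measurement taken prior to the date of the first dose of rescue medication will be used".
- **7.1.8.** Subjects "who do not demonstrate achieving therapeutic" response at the timepoint "or are rescued will count as treatment failures from that timepoint".
- **7.5.3.** "For efficacy analyses, missing observations will not be imputed, except those inherited from the mixed model repeated measures (MMRM").
- **7.5.5.2.** Discontinued or missing subjects are explicitly scored as not achieving response, but only "in subjects from the Short-term Completers Data Set at time points during the LT period".

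Section 7.5.4 keeps every subject with a baseline and any post-baseline assessment. Subjects without a Week 24 value are therefore in the analysis, and that section gives no rule for scoring them.

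**The concern.** A rescued subject whose last pre-rescue HbA1c was below 7.0% is a responder if 7.1.1.3 is followed and a failure if 7.1.8 is followed. No passage ranks the two rules. The only LOCF analysis the SAP defines is for HbA1c change, in 7.5.2: "An ANCOVA analysis using values prior to rescue or treatment discontinuation (LOCF will be used if the week 24 value is not available"). No LOCF responder analysis exists for the response clause in 7.1.1.3 to govern.

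For an unrescued subject with no Week 24 value the text is ambiguous rather than conflicting. Such a subject could be carried forward (7.1.1.3), failed (7.1.8, if failing to demonstrate response includes having no value) or left missing (7.5.3).

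The choice changes response rates when some carried values are below 7%. It changes the treatment difference when missingness, or the carried values themselves, differ between arms. Differing carried values are plausible here. Section 2.2 has insulin titrated over 8 weeks and the comparator not titrated, so early carried values come from different stages of treatment. Section 2.3 makes the trial open-label, with sponsor personnel unblinded to allocation, so the rule should be settled in writing before any by-arm analysis.

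**Working it through.** **The plan's own figure.** The SAP gives no sample size or power for the response endpoints. Its primary calculation (section 5: margin 0.30%, SD 1.1%, one-sided 0.025, 90% power) reproduces: 2 × (1.96 + 1.2816)² × 1.1² / 0.30² = 282.5, so 283 per arm against the stated 284. Power at 284 is 0.901, and 284 / 0.95 gives 299. It is not in dispute and is used here only for the arm size.

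**Set-up.** All rates below are assumptions. Let p be response among subjects with a usable value, m the share rescued or missing, and l the share of carried values below 7%.

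- Response rate = (1 − m)p + ml under LOCF, and (1 − m)p under failure scoring.
- d = saxa-dapa minus insulin. The shift in d, LOCF minus failure, is m_t·l_t − m_c·l_c, where t is saxa-dapa and c is insulin.
- SE = √[p_t(1 − p_t)/n + p_c(1 − p_c)/n], where p_t and p_c are the resulting response rates and n = 299, unadjusted.
- Chance of meeting the margin for secondary 5 = Φ((d + 0.10)/SE − 1.96). Non-inferiority is read as insulin's rate exceeding saxa-dapa's by less than 10 points.

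**Rescue only, secondary 5, p = 30% in both arms.** Rescued 10% (saxa-dapa) vs 3% (insulin), l = 5%:

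- LOCF: 0.90 × 0.30 + 0.10 × 0.05 = 0.275, and 0.97 × 0.30 + 0.03 × 0.05 = 0.2925. d = −1.75 points, chance 61%.
- Failure: 0.270 vs 0.291. d = −2.1 points, chance 58%.
- With l = 10% the shift is (0.10 − 0.03) × 0.10 = 0.7 point, the largest in these cases. With equal rescue of 5% it is 0.

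**Missing without rescue, secondary 5, p = 30% in both arms, l = 15%:**

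| Missing, saxa-dapa vs insulin | d, LOCF | d, failure | Shift | Chance, LOCF | Chance, failure |
|---|---|---|---|---|---|
| 15% vs 15% | 0 | 0 | 0 | 78% | 80% |
| 12% vs 8% | −0.6 | −1.2 | 0.6 | 72% | 68% |
| 20% vs 10% | −1.5 | −3.0 | 1.5 | 64% | 50% |

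For the last row, LOCF gives 0.270 vs 0.285 and failure scoring gives 0.240 vs 0.270. Leaving these subjects missing would give 30% vs 30%, so d = 0. At 284 per arm the chances are about 62% and 48%. A one-point shift needs a missingness imbalance of 1/l: 6.7 points at l = 15%, 4 points at 25% and 20 points at 5%.

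**Equal missingness, unequal carried values.** With 15% missing in both arms and l = 20% vs 10%, secondary 5 is +1.5 points under LOCF and 0 under failure scoring (88% vs 80%). With l reversed it is −1.5 vs 0 (64% vs 80%).

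**Secondary 3**, assumed p = 20% vs 12%, carried values at half those rates, missing 20% vs 10%. LOCF: 0.18 − 0.114 = 6.6 points. Failure: 0.16 − 0.108 = 5.2 points. Power, Φ(d/SE − 1.96), is 63% vs 46%.

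**The case against.** The strongest defence is that 7.1.8 governs on any ordinary reading. It is the section written for these proportions, whereas the 7.1.1.3 paragraph applies only when ANOVA-type models with LOCF are used. The ranked response endpoints are analysed by logistic regression or the covariate-adjusted method named in 7.1.8 and 7.5.4. A reader might infer that the SAP flatly contradicts itself on rescued subjects. The conditional opening of the 7.1.1.3 paragraph does not support a reading that strong. What survives is that 7.1.1.3 names the response endpoint, no LOCF responder analysis exists for it to describe, and precedence is never stated.

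A second defence is that a subject with no Week 24 HbA1c naturally fails to demonstrate response, and that classifying a subject as a failure is not imputing a value, so 7.5.3 need not conflict. That is a fair reading of 7.1.8, but the text does not say it. Where the authors wanted missing to mean non-response, in 7.5.5.2, they wrote it out, and for a different analysis only.

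Third, the larger swings rest on undocumented inputs: twofold differences between arms in missingness or in carried response. This is correct. The milder case moves 0.6 point. Using 299 rather than 284 per arm raises the stated chances by about 2 points and leaves the contrast between rules almost unchanged.

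**Conclusion.** The point holds as unreconciled scoring text on two ranked endpoints, and it should be corrected. The rescue conflict by itself is probably minor: 0.7 point at most in the cases assumed, against a 10-point margin. The missing Week 24 value is the more consequential gap. Its effect on secondary 5 runs from nothing (equal missingness and equal carried response) through 0.6 point to 1.5 points, where the chance of meeting the margin is 64% or 50% depending on the rule.

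A reader might infer that the choice of rule will decide these tests. The documents do not support that. They give no rescue, missingness or response rates, the direction can go either way, and the figures are illustrations only. What they do support is that two analysts following stated text could score the same subject oppositely.

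**What to change.** Before any by-arm analysis:

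1. State in 7.1.8 and 7.5.4 that 7.1.8 governs both ranked responder endpoints, and that a subject without a valid pre-rescue HbA1c in the Week 24 window counts as a non-responder. Validity would follow the 8-day post-dose limit in 8.3.1.
2. Delete the reference to the glycemic response endpoint from the LOCF paragraph in 7.1.1.3, or label it a sensitivity analysis.
3. State that the no-imputation sentence in 7.5.3 does not apply to responder scoring.

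Minor clean-up: correct Week 4 to Week 24 in 7.1.1.3, and square the 7.5.3 sentence with the LOCF ANCOVA in 7.5.2. An LOCF responder result may be shown as an optional sensitivity analysis.

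The cost is a few sentences of SAP wording and, if wanted, one table per endpoint. The downside is lower response rates in both arms wherever carried values would have been below 7%. With equal dropout the absolute 10-point margin also becomes slightly easier to meet (78% to 80% at 15% missing in both arms). With unequal dropout, failure scoring can move the result either way.
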